4.4 End of study definition

The end of study is defined as the last expected visit/contact of the last subject undergoing the study.

The study may be terminated at individual study sites if the study procedures are not being performed according to GCP, or if no patients are recruited. Patients from terminated sites will have the opportunity to be transferred to another site to continue the study. AstraZeneca may also terminate the entire study prematurely if concerns for safety arise within this study or in any other study with dapagliflozin, or due to recommendation by the DMC. Regardless of the reason for termination, all data required by the protocol at the time of discontinuation of follow-up will be collected. In terminating the study, the Sponsor will ensure that adequate consideration is given to the protection of the patients' interests.

See Appendix [A 6](#) for guidelines for the dissemination of study results.

5. STUDY POPULATION

Prospective approval of protocol deviations to recruitment and enrolment criteria, also known as protocol waivers or exemptions, is not permitted.

In this protocol, 'enrolled' patients are defined as those who sign the informed consent form (ICF) and received E-Code. The ICF process is described in Appendix [A 3](#). 'Randomised' patients are defined as those who undergo randomisation and receive a randomisation code.

Patients are eligible to be randomised in the study only if all of the following inclusion criteria and none of the exclusion criteria apply. Enrolled patients who for any reason are not randomised are considered screen failures (see Section [5.4](#)).

5.1 Inclusion criteria

Subjects are eligible to be randomised in the study only if all of the following inclusion criteria and none of the exclusion criteria apply:

1. Provision of signed informed consent prior to any study specific procedures.
2. Male or female patients age ≥ 40 years.
3. Documented diagnosis of symptomatic heart failure (NYHA class II-IV) at enrolment, and a medical history of typical symptoms/signs² of heart failure ≥ 6 weeks before enrolment with at least intermittent need for diuretic treatment.
4. Left Ventricular Ejection Fraction (LVEF) $> 40\%$ and evidence of structural heart disease (i.e. left ventricular hypertrophy or left atrial enlargement³) documented by the most recent echocardiogram, and/or cardiac MR within the last 12 months prior to enrolment. For patients with prior acute cardiac events or procedures that may reduce LVEF, e.g. as defined in exclusion criterion 6, qualifying cardiac imaging assessment at least 12 weeks following the procedure/event is required.
5. NT-pro BNP ≥ 300 pg/ml at Visit 1 for patients without ongoing atrial fibrillation/flutter. If ongoing atrial fibrillation/flutter at Visit 1, NT-pro BNP must be ≥ 600 pg/mL.
6. Patients may be ambulatory, or hospitalized; patients must be off intravenous heart failure therapy (including diuretics) for at least 12 hours prior to enrolment and 24 hours prior to randomisation.

² Typical symptoms associated with heart failure: breathlessness, orthopnoea, paroxysmal nocturnal dyspnoea, reduced exercise tolerance, fatigue, tiredness, increased time to recover after exercise, ankle swelling;

Signs associated with Heart Failure:

More specific: elevated jugular venous pressure, hepatojugular reflex, third heart sound (gallop rhythm), laterally displaced apical impulse

Less specific: weight gain (> 2 kg/week), weight loss (in advanced HF), tissue wasting (cachexia), cardiac murmur, peripheral oedema (ankle, sacral, scrotal), pulmonary crepitations, reduced air entry and dullness to percussion at lung bases (pleural effusion), tachycardia, irregular pulse, tachypnoea, cheyne stokes respiration, hepatomegaly, ascites, cold extremities, oliguria, narrow pulse pressure

³ Left Atrial Enlargement defined by at least 1 of the following: LA width (diameter) ≥ 3.8 cm or LA length ≥ 5.0 cm or LA area ≥ 20 cm² or LA volume ≥ 55 mL or LA volume index ≥ 29 mL/m². Left Ventricular Hypertrophy defined by septal thickness or posterior wall thickness ≥ 1.1 cm

5.2 Exclusion criteria

1. Receiving therapy with an SGLT2 inhibitor within 4 weeks prior to randomisation or previous intolerance to an SGLT2 inhibitor.
2. Type 1 diabetes mellitus (T1D).
3. eGFR <25 mL/min/1.73 m² (CKD-EPI formula) at Visit 1.
4. Systolic blood pressure (BP) <95 mmHg on 2 consecutive measurements at 5-minute intervals, at Visit 1 or at Visit 2.
5. Systolic BP ≥160 mmHg if not on treatment with ≥3 blood pressure lowering medications or ≥180 mmHg irrespective of treatments, on 2 consecutive measurements at 5-minute intervals, at Visit 1 or at Visit 2.
6. MI, unstable angina, coronary revascularization (percutaneous coronary intervention (PCI) or coronary artery bypass grafting (CABG)), ablation of atrial flutter/fibrillation, valve repair/replacement within 12 weeks prior to enrolment. Before enrolment, these patients must have their qualifying echocardiography and/or cardiac MRI examination at least 12 weeks after the event.
7. Planned coronary revascularization, ablation of atrial flutter/fibrillation and valve repair/replacement.
8. Stroke or transient ischemic attack (TIA) within 12 weeks prior to enrolment.
9. Probable alternative or concomitant diagnoses which in the opinion of the investigator could account for the patient's HF symptoms and signs (e.g. anaemia, hypothyroidism).
10. Body mass index >50 kg/m².
11. Primary pulmonary hypertension, chronic pulmonary embolism, severe pulmonary disease including COPD (i.e., requiring home oxygen, chronic nebulizer therapy or chronic oral steroid therapy, or hospitalisation for exacerbation of COPD requiring ventilatory assist within 12 months prior to enrolment).
12. Previous cardiac transplantation, or complex congenital heart disease. Planned cardiac resynchronisation therapy.
13. HF due to any of the following: known infiltrative cardiomyopathy (e.g. amyloid, sarcoid, lymphoma, endomyocardial fibrosis), active myocarditis, constrictive pericarditis, cardiac tamponade, known genetic hypertrophic cardiomyopathy or obstructive hypertrophic cardiomyopathy, arrhythmogenic right ventricular cardiomyopathy/dysplasia (ARVC/D), or uncorrected primary valvular disease.

14. A life expectancy of less than 2 years due to any non-cardiovascular condition, based on investigator's clinical judgement.
15. Inability of the patient, in the opinion of the investigator, to understand and/or comply with study medications, procedures and/or follow-up OR any conditions that, in the opinion of the investigator, may render the patient unable to complete the study.
16. Active malignancy requiring treatment (with the exception of basal cell or squamous cell carcinomas of the skin).
17. Acute or chronic liver disease with severe impairment of liver function (e.g., ascites, oesophageal varices, coagulopathy).
18. Women of child-bearing potential (i.e. those who are not chemically or surgically sterilised or post-menopausal) not willing to use a medically accepted method of contraception considered reliable in the judgment of the investigator OR who have a positive pregnancy test at randomisation OR who are breast-feeding.
19. Involvement in the planning and/or conduct of the study (applies to both AstraZeneca personnel and/or personnel at the study site).
20. Previous randomisation in the present study.
21. Participation in another clinical study with an IP or device during the last month prior to enrolment.

5.3 Lifestyle restrictions (not applicable)

5.4 Screen failures

Enrolled patients who are found not eligible (i.e. not meeting all the inclusion criteria or fulfilling any of the exclusion criteria) must not be randomised or initiated on treatment.

Screen failures are defined as patients who signed the informed consent form to participate in the study but are not subsequently randomised. A minimal set of screen failure information is required to ensure transparent reporting of screen failure patients to meet the Consolidated Standards of Reporting Trials (CONSORT) publishing requirements and to respond to queries from regulatory authorities. Minimal information includes demography, eligibility criteria (reason for screen failure), and any serious adverse event (SAE).

Screen failures may be re-enrolled one time during the study if the Investigator considers that the patient may be eligible for participation in this study at another time point. Re-enrolled patients should be assigned the same enrolment code as for the initial enrolment. All enrolment assessments and procedures, including signing the informed consent form, should be performed again.

5.5 Procedures for handling of randomized not eligible patients

If a patient is randomised and later found not eligible, the Investigator should immediately inform the AstraZeneca representative, who will report the protocol deviation to the AstraZeneca Study Physician.

Study treatment must be discontinued in all cases where continued treatment is deemed to pose a safety risk to the patient. Regardless of whether study treatment is discontinued or not, the patient should continue his/her participation in the study for follow-up of endpoints and other protocol-defined study procedures until the end of the study. Consistent with the intention-to-treat principle, all randomised patients are included in the efficacy analysis according to randomised treatment assignment. The AstraZeneca Study Physician must ensure that the protocol deviation and the rationale for the decision to discontinue or continue study treatment are appropriately documented.

6. STUDY TREATMENTS

Study treatment is defined as any investigational product(s) (including marketed product comparator and placebo) or medical device(s) intended to be administered to a study participant according to the study protocol. Study treatment in this study refers to dapagliflozin or matching placebo.

6.1 Treatments administered

Table 4 Study Treatments

	Dapagliflozin	Placebo
Investigational Product name	Dapagliflozin 10 mg	Matching placebo 10 mg
Dosage formulation	Green, diamond shaped, film coated tablets 10 mg	Green, diamond shaped, film coated tablets 10 mg placebo
Route of administration	Oral	Oral
Dosing instructions	Once daily	Once daily
Packaging and labeling	Investigational Product will be provided in bottles. Each bottle will be labelled in accordance with Good Manufacturing Practice Annex 13 and per country regulatory requirements	Investigational Product will be provided in bottles. Each bottle will be labelled in accordance with Good Manufacturing Practice Annex 13 and per country regulatory requirements
Provider	AstraZeneca	AstraZeneca

The tablets contain lactose, in quantities not likely to cause discomfort in lactose-intolerant individuals.

6.2 Preparation/handling/storage/accountability

The investigator or designee must confirm appropriate temperature conditions have been maintained during transit for all study treatment received and any discrepancies are reported and resolved before use of the study treatment.

All investigational product (IP) should be kept in a secure place under appropriate storage conditions. The label on the IP bottle specifies the appropriate storage.

Only patients randomised in the study may receive IP and only authorised site staff may supply or administer IP. The administration of all investigational products should be recorded in the appropriate sections of the eCRF.

The Investigator is responsible for IP accountability, reconciliation, and record maintenance (i.e. receipt, reconciliation, and final disposition records).

The investigator will retain the returned IP until the AZ representative or delegate collects it, along with any IP not dispensed. The AZ representative or delegate is responsible for confirming the investigator or delegate has recorded the quantities of returned and unused tablets at a patient level before IP is destroyed. The AZ representative or delegate will advise on the appropriate method for destruction of unused IP.

6.3 Measures to minimise bias: randomisation and blinding

All patients will be centrally assigned to randomised IP using an interactive voice/web response system (IxRS). Randomisation to IP will be performed in balanced blocks to ensure approximate balance between the treatment groups (1:1). The randomisation codes will be computer generated and loaded into the IxRS database. Before the study is initiated, the telephone number and call-in directions for the IxRS and/or the log-in information and directions for the IxRS will be provided to each site.

If a randomised patient withdraws from the study, then his/her enrolment/randomisation code cannot be reused. Withdrawn randomised patients will be included in the intention to treat analysis.

The IxRS will provide the Investigator with the kit identification number to be allocated to the patient at each dispensing visit. At all visits where IP is dispensed, site personnel will do a kit verification in IxRS before providing the IP bottle to the patient. Routines for this will be described in the IxRS user manual that will be provided to each centre.

The blinding of treatment is ensured by using a double-blind technique. Individual treatment codes, indicating the randomised treatment for each patient, will be available to the investigator(s) or pharmacists from the IxRS. Instructions for code breaking/unblinding will be described in the IxRS user manual that will be provided to each site.

The randomisation code should not be broken except in medical emergencies when the appropriate management of the patient requires knowledge of the treatment randomisation. The Investigator is to document and report the action to AstraZeneca, without revealing the treatment given to the patient to the AstraZeneca staff.

AstraZeneca retains the right to break the code for SAEs that are unexpected and are suspected to be causally related to an investigational product and that potentially require expedited reporting to regulatory authorities. Randomisation codes will not be broken for the planned analyses of data

until all decisions on the evaluability of the data from each individual patient have been made and documented.

6.3.1 Stratification and capping

The recruitment will be continuously monitored in order to achieve adequate proportions of patient sub-populations.

6.3.1.1 Stratification

Randomisation will be stratified in IxRS based on patients with and without T2D at the time of randomisation in order to ensure approximate balance between treatment groups within each sub-population. Stratification on T2D at the time of randomisation is based on:

- Established diagnosis of T2D

OR

- HbA1c $\geq 6.5\%$ (48 mmol/mol) shown at central laboratory test at enrolment (Visit 1)

6.3.1.2 Capping

The intent is to enrol a typical cross-section of patients with HFpEF and to include representative proportions of diabetic and non-diabetic patients. The number of randomised patients with and without T2D will be monitored in order to ensure a minimum of 30% in each sub-population. Randomisation may be capped (i.e., no more patients can be randomised in a specific sub-population) if the pre-determined limit is reached.

Randomisation of patients based on geographic region will be monitored to ensure global representation. LVEF value, NYHA class, subacute subgroup (i.e. randomised in- hospital or within 30 days from discharge) and atrial fibrillation status at Visit 1 may be capped in IxRS to avoid over- or under-representation of these patient subgroups.

6.4 Treatment compliance

The administration of all IP should be recorded in the appropriate sections of the eCRF. Any change from the dosing schedule should be recorded in the eCRF.

Patients will be asked to return all unused IP and empty packages to the clinic at the site visit except Visit 3. At each visit, any patient found to be non-compliant will be counselled on the importance of taking their IP as prescribed. The investigator or delegate will enter the number of returned tablets in the eCRF.

The Investigational Product Storage Manager is responsible for managing IP from receipt by the study site until the destruction or return of all unused IP. The Investigator(s) is responsible for ensuring that the patient has returned all unused IP.

6.5 Concomitant therapy

All patients should be treated according to regional standard of care of HFpEF and existing comorbidities (including treatment of hypertension, ischemic heart disease, atrial fibrillation, diabetes, hyperlipidaemia). Background medications should be part of clinical practice and will not be provided by the Sponsor.

6.5.1 Prohibited medication

Concomitant treatment (i.e., treatment in combination with IP) with open label SGLT2 inhibitors e.g., dapagliflozin, empagliflozin, canagliflozin, ertugliflozin, tofogliflozin and luseogliflozin and fix dose combinations containing these drugs should not be used. Also in situations when the patient is not on IP, treatment with open label SGLT2 inhibitors during the study could interfere with the interpretation of study results. If treatment with an SGLT2 inhibitor alone or in combination is deemed essential, IP must be discontinued before that treatment is started.

6.5.2 Recording of concomitant treatment

Recording of relevant concomitant medications in the eCRF will be made according to the schedule of activities ([Table 1](#)). These include medications for cardiovascular conditions as well as diabetes mellitus.

6.5.3 Heart failure background standard of care

The patients should be on background standard of care therapies for patients with HFpEF according to local guidelines, including diuretics when needed to control symptoms and volume overload and adequate treatment of co-morbidities such as hypertension and ischaemic heart disease.

6.5.4 Anti-diabetes treatment

6.5.4.1 Background

More than 40% of patients with established HF are estimated to have T2D ([Kristensen et al 2016](#)). Therefore, it is expected that a large proportion of patients will have an established T2D diagnosis when included in this study and that some patients will develop T2D during the course of the study. Treatment of diabetes should follow established guidelines, such as according to glycaemic goals as recommended by the American Diabetes Association (ADA) and European Association for the Study of Diabetes (EASD) in their joint Position Statement ([Inzucchi et al 2012](#), [Inzucchi et al 2015](#)).

6.5.4.2 Treatment of patients with established diagnosis of type 2 diabetes

Diabetes medications at baseline and during the study will be recorded in the eCRF. Patients with T2D at randomisation will continue their T2D treatment. SGLT2-inhibitors should be avoided (see Section [6.5.1](#)). Patients treated with insulin or insulin secretagogues have a higher risk of experiencing hypoglycaemic events compared with those treated with other antidiabetic agents. If needed, T2D treatments may be adjusted at the discretion of the Investigator or diabetes health care provider.

6.5.5 Other concomitant treatment

Medications other than described above, which is considered necessary for the patient's safety and wellbeing, may be given at the discretion of the Investigator.

6.6 Dose modification (not applicable)

6.7 Treatment after the end of the study

The patients will stop taking IP at the study closure visit (SCV). Remaining IP will be collected at that time. Post-study treatment will not be provided by the Sponsor. Patients should receive standard of care therapy after the SCV, at the discretion of the Investigator.

7. DISCONTINUATION OF TREATMENT AND SUBJECT WITHDRAWAL

7.1 Discontinuation of study treatment

Discontinuation from study treatment is NOT the same thing as a withdrawal from the study. If the patient temporarily or permanently discontinues IP, the patient should remain in the study and it is important that the scheduled study visits and data collection continue according to the study protocol until study closure.

Patients may be discontinued from IP in the following situations:

- Contraindication to further dosing with IP, in the opinion of the Investigator, such as Adverse event or other safety reasons.
- Severe non-compliance with the study protocol.
- Diabetic ketoacidosis (DKA). Consider temporarily interrupting IP if DKA is suspected. If DKA is confirmed, IP should be discontinued permanently.
- Positive pregnancy test (discontinue IP and notify Sponsor representative).
- Patient decision. The patient is at any time free to discontinue treatment, without prejudice to further treatment.

See the [Table 1](#) for data to be collected at the time of treatment discontinuation and follow-up and for any further evaluations that need to be completed.

7.1.1 Temporary discontinuation

Every attempt should be made to maintain patients on IP during the course of the study. If IP has been interrupted, it should be re-introduced as soon as, in the opinion of the Investigator, the patient's condition is stable.

7.1.1.1 Unexpected acute declines in eGFR

If an unexpected, acute decline in kidney function is observed, the patient should be evaluated and temporary interruption of IP should be considered. Volume depletion, hypotension, inter-current medical problems and concomitant drugs may cause increases in blood creatinine. Urinary tract infection and urinary obstruction should be considered (the latter especially in men). Several drugs may cause a decline in kidney function, especially non-steroidal anti-inflammatory drugs (NSAID) and certain antibiotics such as trimethoprim. If any drug is suspected of causing or contributing to worsening kidney function, their use should be re-considered.

7.1.1.2 Volume depletion/hypotension

Patients with clinically relevant symptoms/signs of suspected volume depletion and/or hypotension, should in addition to considering temporary interruption of IP have their regular medication reviewed, and consideration given to reducing the dose of, or stopping concomitant medications, as assessed on an individual basis, including diuretics and drugs that lower blood pressure. The need for conventional diuretics (or the dose of diuretic used) should be re-evaluated in light of the patient's symptoms and signs.

7.1.1.3 Patients at risk of volume depletion

Temporary interruption of IP may be considered in patients thought to be at risk of volume depletion/hypotension, such as patients with an acute medical illness potentially causing volume depletion because of inadequate fluid intake or fluid/blood loss (e.g. gastroenteritis, gastrointestinal haemorrhage), or those undergoing major surgery.

7.1.2 Procedures for discontinuation of study treatment

Investigators should instruct their patients to contact the site before or at the time IP is stopped. A patient that decides to discontinue IP will always be asked about the reason(s) and the presence of any AEs. Generally, AEs, SAEs, and potential endpoint events should not lead to IP discontinuation, unless there is a clear clinical rationale to do so.

The date of last intake of IP should be documented in the eCRF. All IP should be returned by the patient at their next on-site study visit or unscheduled visit. Patients permanently discontinuing IP should be given locally available standard of care therapy, at the discretion of the Investigator.

Discontinuation of IP, for any reason, does not impact on the patient's participation in the study. The patient should continue attending subsequent study visits and data collection should continue according to the study protocol. If the patient does not agree to continue in-person study visits, a modified follow-up must be arranged to ensure the collection of endpoints and safety information. This could be a telephone contact with the patient, a contact with a relative or treating physician, or information from medical records. The approach taken should be recorded in the medical records. A patient that agrees to modified follow-up is not considered to have withdrawn from the study.

Restart of randomised IP is always encouraged. Even if a premature treatment discontinuation visit (PTDV) was completed due to discontinuation of IP, this should not prevent the patient to return to randomised IP if deemed appropriate.

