8.2.7 Premature Treatment Discontinuation Visit

Patients who prematurely and permanently discontinue treatment with IP should return for a premature treatment discontinuation visit (PTDV), which will be done as soon as possible after last dose of IP. The following assessments and procedures will be conducted:

- KCCQ, PGIS and EQ-5D-5L questionnaire will be completed
- NYHA Functional Classification will be evaluated
- Vital signs (BP, pulse) and weight will be assessed and recorded
- Review and updating of concomitant medication and recording of relevant medications
- Review and recording of any cardiac and HF related procedures

- Review of potential efficacy and safety events including COVID-19 testing results
- If the patient has experienced any potential endpoints, SAEs, DAEs and/or amputations, adverse events (AEs) leading to amputation and potential risk factor AEs for amputations affecting lower limbs since the last visit, this will be recorded in the eCRF
- Drug accountability of the returned IP will be checked

Patients who discontinue treatment prematurely should attend all study visits according to plan, including the study closure visit (SCV). Patients may re-start treatments if assessed as appropriate by the Investigator. For further details regarding discontinuations from IP, please see Section 7.1.

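### Section 7.1.2 encourages restart of study drug without exception, while Section 7.1 makes the stop after confirmed diabetic ketoacidosis permanent; the two must be reconciled

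*Protocol*

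**What the plan says.** Section 7.1 lists situations for stopping investigational product (IP) under a permissive lead-in: "Patients may be discontinued from IP in the following situations". The DKA item has two steps. For suspicion: "Consider temporarily interrupting IP if DKA is suspected". For confirmation: "If DKA is confirmed, IP should be discontinued permanently".

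Section 7.1.1 deals with temporary discontinuation. Interrupted drug is to be resumed once the investigator considers the patient stable.

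Section 7.1.2 sets out procedures when IP is stopped. Its last paragraph opens: "Restart of randomised IP is always encouraged". On a patient who has already had a PTDV, it says "this should not prevent the patient to return to randomised IP if deemed appropriate".

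Section 8.2.7 assigns the PTDV to patients whose stop is both premature and permanent. It then says: "Patients may re-start treatments if assessed as appropriate by the Investigator". The sentence after that reads: "For further details regarding discontinuations from IP, please see Section 7.1".

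**The concern.** After confirmed DKA, a site finds one sentence that makes the stop permanent and another that encourages restart in every case. Section 7.1.2 neither excepts the DKA stop nor refers to the item that governs it. Section 7.1 does not say that its DKA item overrides the restart sentence.

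What is at stake is consistent handling of a safety event. The protocol gives DKA its own eCRF pages, a definition (Section 8.5.1.2.1) and an independent adjudication committee (Section 8.5.1.2.2). The study is planned for roughly 400 to 500 sites (Section 4.1), and an instruction on drug exposure after such an event should read the same way at all of them.

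**Working it through.** No arithmetic applies. The point depends on no sample size, alpha, power or event count, and the plan has no figure to reproduce. The check is a comparison of the passages.

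| Place | Stop it addresses | What it says about going back on drug | Confirmed DKA excepted? |
|---|---|---|---|
| 7.1, DKA item | Confirmed DKA | Nothing; the stop is permanent | This is the DKA rule itself |
| 7.1.1 | Temporary interruption | Resume when stable, in the investigator's opinion | Not relevant to a permanent stop |
| 7.1.2, first restart sentence | Not limited | Always encouraged | No |
| 7.1.2, second restart sentence | Stop followed by a PTDV | Not prevented, if deemed appropriate | No |
| 8.2.7 | Premature and permanent stop | Allowed, if the investigator assesses it as appropriate | No, but refers to 7.1 for discontinuations |

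**Step 1. Can the restart text be read as covering temporary stops only?** No. Resumption after a temporary interruption already has its own rule in Section 7.1.1. Section 7.1.2 expressly carries return to drug over to patients who have completed a PTDV, and Section 8.2.7 gives that visit to patients who stop permanently. The restart text is therefore written with permanent stops in view.

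**Step 2. Does a stop for confirmed DKA fall in that group?** Yes. Section 7.1 calls it permanent. Unless it coincides with study closure it is also premature, so Section 8.2.7 applies.

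**Step 3. Do the conditions remove the conflict?** Only in part. The second restart sentence of 7.1.2 and the sentence in 8.2.7 depend on appropriateness, and a reader may hold that restart is not appropriate where 7.1 makes the stop permanent. The first restart sentence of 7.1.2 carries no condition. The direct clash is between that sentence and the DKA item in 7.1.

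**Step 4. Does the cross-reference in 8.2.7 settle it?** It helps, because it sends the reader towards the section holding the DKA rule. But it concerns discontinuation and is silent on what limits restart. Section 7.1.2 is itself part of Section 7.1, so a reader who follows the reference meets both the permanent stop and the unqualified encouragement. Section 7.1.2 has no corresponding reference to the DKA item.

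**Step 5. Is the DKA item firm enough to decide the matter alone?** It is specific, but it sits under a lead-in that says patients may be discontinued, which leaves some doubt about how binding the list is.

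**The case against.** The strongest reply is that a specific rule normally prevails over a general one. Only one item in Section 7 names DKA, and a site managing a confirmed case would look there. The restart sentence in 7.1.2 is a general retention message that follows text on keeping patients in follow-up, and it does not claim to override its parent section. Many permanent stops follow from patient decision, non-compliance or investigator judgement, where a later return to drug is unremarkable and a policy of encouraging it is coherent. Appendix B 7, in the guide to causality, adds that the sponsor would ordinarily neither recommend nor support a re-challenge. That guide does not govern restart, but it makes a literal reading of the encouragement less plausible.

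Much of this stands. It confines the tension to confirmed DKA and makes Section 8.2.7 the weaker limb. It does not remove the conflict between 7.1 and 7.1.2, because the protocol nowhere states that the specific rule prevails, and the encouraging sentence is worded to admit no exception.

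A reader might infer two stronger claims that the protocol does not support:

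- **That three sections allow or encourage restart after any stop, whatever the circumstances.** The PTDV sentence in 7.1.2 and the sentence in 8.2.7 are both conditional, and neither requires restart in any patient.
- **That the safety summaries would be distorted.** Section 9.4.2 plans summaries both on treatment and over all observations regardless of treatment. With no DKA frequency given, any effect on the on-treatment version is speculation.

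**Conclusion.** The point holds as a conflict between two stated instructions on a patient-safety rule: the permanent stop in Section 7.1 and the unqualified encouragement to restart in Section 7.1.2. Section 8.2.7 is secondary. It does not contradict 7.1 outright, but it offers restart to the group that includes these patients without saying that the DKA rule limits the offer.

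The consequence is for conduct, not inference. The primary analysis follows the intention-to-treat principle on all randomised patients (Section 9.4.1.1) and does not depend on restart. The number of patients concerned is unknown and may be small.

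The conclusion assumes only that some sites would take the encouraging sentence at its word. A careful site could well treat the DKA item as governing, but the protocol leaves that to inference. The inconsistency should be corrected. It is not a reason to doubt the design or the analysis.

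**What to change.** The sponsor should reconcile Sections 7.1 and 7.1.2. The restart sentence in 7.1.2 should be qualified by an explicit statement, with a cross-reference to the DKA item, of whether it applies to a stop that Section 7.1 calls permanent. The restart sentence in 8.2.7 should be aligned with it. Its existing reference to Section 7.1 can stay, provided the text makes clear whether that section limits restart as well as governing discontinuation. Which clinical rule holds is for the sponsor's medical team, and none is proposed here.

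The cost is about one sentence in each of two sections, plus a communication to sites so that all apply the same rule. No analysis, sample size or data collection changes.
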